### **9.2.4. Standard Analyses**

#### **Study Conduct and Patient Disposition**

An accounting of the study patients will be tabulated. The subject evaluation groups will be listed. The Full Analysis Set will be used.

Subject discontinuation from treatment and study will be tabulated and listed separately with their reason for discontinuation. The Safety Analysis Set will be used.

#### **Baseline Characteristics**

Baseline characteristics such as demographics, prior medication, medical history, ECOG performance status, and primary diagnosis will be tabulated and listed. The Safety Analysis Set will be used.

#### **Treatment Administration/Compliance**

Listings and tables by dose level will be provided. Cycle length is 21 days. Day 1 of a cycle is the first date of dose within that cycle. The safety analysis set will be used.

Dose modifications may occur in the following ways:

- Cycle delay—Day 1 of current cycle starts later than 21 days from Day 1 of the previous cycle (only applies to cycle 2 and above);
- Dose reduction—A decrease in the administered total daily dose (non-zero) compared to the planned total daily dose upon enrollment.

Intra-patient dose escalation is not allowed in this study. The following will be summarized by subject for each dose level:

- Number of subjects per dose level.
- Median and range of number of cycles started per subject.
- Number (%) of subjects starting a cycle (1, 2, 3...).
- Number (%) of subjects with cycle delays.
- Number (%) of dose interruptions (include both known and unknown dates).
- Number (%) of subjects with dose reductions.
- Number (%) of each reason (AE vs. Other) for cycle delays, dose interruptions and dose reductions.
- Time on treatment (median, range).

The following will be summarized by cycle received for each dose level:

- Total number of cycles started.
- Number of cycles started per subject (median, range).
- Number of cycles before 1st delay (median, range).
- Number of cycles before 1st reduction (median, range).
- Number of cycles before 1st interruption (median, range).

The following will be summarized for cumulative dose by dose level and cycle:

- Summary statistics (mean, median, standard deviation and range) of cumulative dose and percent of starting dose (compared to Day 1 dose of each cycle).

Listings by subject (ordered by dose level): start date and stop date of each dosing period within each cycle (including records with 0mg), administered total daily dose for each period, any missed doses with unknown dates (Y/N), number of missed doses with unknown dates, reason for any dosing changes.

Listings by subject and each cycle (ordered by dose level): cycle length, total planned dose, administered total dose, percentage of planned dose, dose delay (yes/no), dose reduction (yes/no), and dose interruption (yes/no).

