5.2.2. Preparation and Dispensing

Only qualified personnel who are familiar with procedures that minimize undue exposure to them and to the environment should undertake the preparation, handling, and safe disposal of chemotherapeutic agents. All preparations should take place under aseptic conditions.

The starting dose level will be 0.2 mg/kg. The patient's actual body weight will be used to calculate the mg/kg dose, and the calculated dose will be rounded off to the first decimal point. Specific preparation and dispensing instructions are provided in the Dosage Administration Instruction (DAI) located in the Study Manual.

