5.2.3. Administration

PF-06650808 will be administered on Day 1 of each 21-day cycle per the DAI as an IV infusion over approximately 60 minutes. A cycle is defined as the time from Day 1 dose to the next Day 1 dose. If there are no treatment delays, a cycle will be 21 days. Each patient may receive PF-06650808 until disease progression, unacceptable toxicity, withdrawal of consent, or study termination.

In the case of infusion related reactions, characterized by fever and chills, and less commonly hypotension, the sponsor should be notified and pre-treatment medication should be administered prior to subsequent infusions (in the case that the patient is able to continue on treatment as per [Appendix 5](#)). The decision to incorporate pre-medication in all patients will be made following discussions between the sponsor and the investigators. Patients should be pre-treated with acetaminophen and diphenhydramine (or other antihistamine) approximately 0.5 to 2 hours before each PF-06650808 administration. The pre-treatment medications will not be supplied by Pfizer.

Suggested starting doses are 650 to 1000 mg acetaminophen and 50 mg diphenhydramine (or equivalent of other antihistamine) IV or oral. Two (2) additional doses of acetaminophen may be administered approximately every 4 hours after the initial pre-treatment or as needed.

PF-06650808 will be administered as a 60-minute (± 5 minutes) IV infusion. The use of an infusion pump is the preferred method of administration to ensure accurate delivery of the investigational product, but gravity drips are allowed. Please refer to the DAI for infusion rate and duration.

Medication errors may result, in this study, from the administration of the wrong drug, by the wrong patient, at the wrong time, or at the wrong dosage strength. Such medication errors occurring to a study participant are to be captured on the medication error case report form (CRF) which is a specific version of the AE page of the CRFs and on the SAE form when appropriate. In the event of medication dosing error, the sponsor should be notified immediately.

Medication errors are reportable irrespective of the presence of an associated AE/SAE, including;

- Medication errors involving patient exposure to the investigational product;
- Potential medication errors or uses outside of what is foreseen in the protocol that do or do not involve the participating patient.

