5.2.6. Dose Reductions

Dose reductions or delays in the administration of PF-06650808 are permitted as described below for PF-06650808 related toxicity. The sponsor should be notified when dose reductions are planned and consulted for any dose reduction related questions.

Once a dose has been reduced for a given patient, all subsequent cycles should be administered at that dose level, unless further dose reduction is required. The reduced dose will be considered the maximum dose for all subsequent cycles for that patient. Doses should be reduced to the next lowest cohort dose level. Dose re-escalation is not allowed.

Patients enrolled in the first cohort should be discontinued from the study if more than 1 dose reduction is required. Patients enrolled in subsequent cohorts should be discontinued from the study if more than 2 dose reductions are required. For patients experiencing an adverse

event related to PF-06650808 that fails to recover to CTCAE Grade 1 (or within 1 grade of starting values for pre-existing laboratory abnormalities) leading to treatment delay of >2 weeks should be discontinued unless discussed with the sponsor.

The following table summarizes the actions following the toxicities observed during the study period.

Event	Action
Grade 3 or 4 nonhematologic toxicity considered at least possibly related to PF-06650808 per investigator judgment (including persistent nausea, vomiting, diarrhea despite optimal medical therapy)	
 Hold PF-06650808 infusion until recovery to Grade 0-1 or baseline and reduce by 1 dose level. Discontinue PF-06650808 if dose delay is more than 2 weeks. If toxicity reoccurs despite reduction, patient may be dose reduced again by another dose level upon recovery to grade 0-1 or baseline unless the patient is in the first dose group, then only 1 dose reduction is allowed. Prompt palliative measures are strongly encouraged (eg, anti-emetics). Patients who experience Grade 4 non hematologic toxicities despite intervention should be discontinued from the study.

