7.1.4. Vital Signs and Physical Examination

Patients will have a physical exam to include weight, vital signs, assessment of ECOG status and height; height will be measured at screening only.

A complete physical examination (PE) will be performed at Screening, Day 1 of Cycle 1, and at the End of Treatment visit for each patient and will include an assessment of all body systems (including neurological examination, genitourinary examination is optional), the measurement of body weight, vital signs and assessment of ECOG performance status. The complete PE on Day 1 of Cycle 1 is not required if the screening complete PE is performed within 72 hours of dosing. Findings of all physical examinations should be recorded in the source documents, and any change from baseline considered by the investigator to be clinically significant should be recorded as an adverse event in the CRF.

Abbreviated PEs, including skin assessment, should be performed as appropriate at each visit where complete physical exams are not required, and on an as needed basis for assessment of adverse events. Abbreviated exams should be targeted to specific symptoms or complaints and be consistent with local standard of care.

Weight and body surface area (BSA) do not need to be performed at each visit; however patients should be monitored throughout the study for significant weight change. If, in the Investigator's opinion, clinically significant weight change occurs, BSA should be recalculated to determine appropriate dose.

Vital signs will include measurements of blood pressure, pulse rate and temperature (oral, tympanic or axillary). On Day 1 of each cycle, vital signs should be measured prior to infusion start (pre-dose) and 1 hour after the start of the infusion. Sitting blood pressure (BP) will be measured with the patient's arm supported at the level of the heart and recorded to the nearest mmHg sufficient. The same arm (preferably the dominant arm) should preferably be used throughout the trial. The blood pressure cuff, which has been properly sized and calibrated, should be used to measure blood pressure. The use of automated devices for measuring BP and pulse rate is acceptable. When the timing of the measurements coincides with a blood collection, blood pressure and pulse rate should be obtained prior to the nominal time of the blood collection.

7.1.5. (12-Lead) ECG

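### The SAP counts any shortfall from the enrolment dose as a dose reduction, so part-given infusions (and, if read in mg, weight-driven changes) are counted although the dose level has not changed

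*SAP*

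**What the plan says.** SAP 9.2.4 recognises two kinds of dose modification, cycle delay and dose reduction. The second is a "decrease in the administered total daily dose (non-zero) compared to the planned total daily dose upon enrollment". The section also tabulates dose interruptions but does not define them. It asks, by dose level, for the number and percentage of patients with reductions, the number of cycles before the first reduction, and reasons split into AE and Other. A by-patient listing covers dosing periods, "including records with 0mg), administered total daily dose for each period". A second listing gives planned dose, administered dose and percentage of planned dose for each cycle.

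The protocol describes the treatment differently. Section 5.2.3: "PF-06650808 will be administered on Day 1 of each 21-day cycle". Section 5.2.2, on how the amount is worked out: "actual body weight will be used to calculate the mg/kg dose, and the calculated dose will be rounded off to the first decimal point". Section 5.2.6 allows reductions for toxicity related to the drug and says how far they go: "Doses should be reduced to the next lowest cohort dose level". Section 7.1.4 says weight need not be taken at every visit, but provides for a recalculation that rests on the investigator's judgement: "clinically significant weight change occurs, BSA should be recalculated to determine appropriate dose".

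**The concern.** The two documents use the same term for different events. In the protocol, a reduction is a deliberate move to a lower assigned level. In the SAP, it is any positive administered amount below a reference fixed at enrolment. The SAP wording (daily dose, dosing periods) suits a drug taken every day better than one infusion per 21-day cycle.

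Two kinds of patient can be counted without having changed level:

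- **Part-given infusion.** Appendix 5 requires the infusion to be stopped and disconnected for a Grade 3 or 4 reaction, and to be stopped if a reaction recurs. The patient received less than planned but was never assigned a lower level. Because interruption is undefined, nothing takes the case out of the reduction count.
- **Weight-driven change.** If the comparison is made in mg, a patient re-dosed at the same mg/kg level after losing weight falls below the enrolment amount. The reference does not move, so every later cycle at the lower weight is flagged as well.

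What is at stake is the descriptive picture of tolerability. A stopped infusion would probably be filed under AE and read as a toxicity reduction, although Protocol 3.3 keeps Grade 3 or higher infusion reactions out of the DLT definition.

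**Working it through.** The plan gives no figure to reproduce here, so the check applies the SAP rule and a dose-level rule to the same cases.

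**Inputs**
- SAP 9.2.4 rule: flag if 0 < A < P, where A is the administered dose and P is the dose planned at enrolment.
- Protocol 5.2.2: P in mg = level (mg/kg) × weight (kg), rounded to 0.1.
- Protocol 3.2: escalation increments of 30%, 69% or 100%.
- Protocol 9.3: about 20 patients in Part 2.
- Assumed for illustration: 2.0 mg/kg and 70 kg, so P = 2.0 × 70 = 140.0 mg. The range tried was 0.2, 2.0 and 6.4 mg/kg with 50, 70 and 90 kg.

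**1. Size of a protocol reduction.** One level down after an increment r is a fall of 1 − 1/(1 + r).
- r = 30%: 1 − 1/1.30 = 23.1%
- r = 69%: 1 − 1/1.69 = 40.8%
- r = 100%: 1 − 1/2.00 = 50.0%

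**2. Part-given infusion, level unchanged.** A = fraction given × 140.0 mg.
- 99%: 138.6 mg
- 95%: 133.0 mg
- 90%: 126.0 mg
- 80%: 112.0 mg

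All four are flagged. In mg/kg the comparison is the same (80% of 2.0 is 1.6, below 2.0), so the unit does not matter. A dose-level rule flags none of them.

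**3. Weight loss with recalculation, level unchanged.**
- 5% loss: 2.0 × 66.5 = 133.0 mg (−5.0%)
- 10% loss: 2.0 × 63 = 126.0 mg (−10.0%)

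Read in mg, both are flagged. Read in mg/kg, the dose is still 2.0 and neither is. In mg, even a 1% recalculated loss is flagged at every dose and weight tried (for example 0.2 mg/kg at 70 kg: 14.0 to 13.9 mg).

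**4. Direction of error.** For weight gain to hide a true one-level reduction in mg, (level/1.3) × new weight must reach level × old weight, a gain of 30% at the narrowest spacing. The miscount is therefore almost entirely upward.

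**5. Effect per patient.** 1/20 = 5 percentage points in Part 2 for each patient wrongly counted; 0 if there are none.

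**The case against.** The strongest reply is that the weight route may not exist. The SAP definition names no unit. What the sponsor specifies at enrolment under Protocol 5.1 is a dose level, and levels are in mg/kg throughout; the tables are also organised by dose level. Read that way, weight loss alone is not flagged. The mg reading is inferred from the word total and from 0mg in a listing, and zero is zero in either unit. Re-dosing for weight also depends on the investigator's judgement under 7.1.4, and the Schedule of Activities lists weight only at screening, Cycle 1 Day 1 and end of treatment. This stands: the weight route is conditional, not established.

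The infusion route is narrow too. After chills and fever or a Grade 2 reaction, Appendix 5 has the infusion resumed at half rate, so the full dose may still be given. After a Grade 3 or 4 hypersensitivity reaction treatment ends, so no later cycles are distorted. That limits the number of cases but does not remove them.

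The listings let a careful reader trace individual cases through the reason for change and the percentage of planned dose. This is true, but the summary counts would still include them.

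**Conclusion.** The point holds as a minor one. The SAP states a rule that, followed literally, counts events the protocol does not call reductions. For part-given infusions this is so under either unit; for weight change only if the dose is compared in mg and has been recalculated. The rule is triggered by a shortfall of 1%, whereas the smallest one-level step on the 30% grid is 23.1%.

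The number of patients affected cannot be derived from the documents and may be zero. Three stronger conclusions that a reader might draw are not supported:

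- That a set share of Part 2 will be misreported. Supposing 20–30% of 20 patients are re-weighed lower gives 4 to 6 patients, but nothing in the documents supports that share.
- That weight loss will certainly be reported as a reduction. The unit is not stated.
- That choice of the RP2D is compromised. Protocol 3.4 refers to feasibility of long-term administration and does not mention reduction counts. AEs, laboratory grades, discontinuations, delays and time on treatment are summarised separately.

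No DLT, MTD or response analysis uses the flag. The effect is confined to the descriptive exposure tables.

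**What to change.** In SAP 9.2.4:

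- Define a dose reduction as an assigned mg/kg dose level, in any cycle, below the level assigned at enrolment.
- Report incomplete infusions as a separate category, with the percentage of that cycle's planned dose given, and define dose interruption so that the two do not overlap.
- State that a change in mg caused by weight at an unchanged level is not a reduction.

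Under this definition none of the examples in steps 2 and 3 of the working is flagged, while every true step down (23.1%, 40.8% or 50.0%) still is.

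Separately, Protocol 5.2.2 (mg/kg on actual body weight) and 7.1.4 (recalculation through body surface area) contradict each other on how dose is recalculated and must be reconciled by the sponsor.

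For the SAP the cost is a wording change and one altered derivation. The sponsor already assigns the dose level, and percentage of planned dose is already listed by cycle, so no new data are needed.

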3.4. Recommended Phase 2 Dose (RP2D) Definition

The RP2D is the dose chosen for further study based on Phase 1 results. If the MTD proves to be clinically feasible for long term administration in a reasonable number of patients, such dose usually becomes the RP2D. Further experience with the MTD may result in a RP2D dose lower or higher than the MTD.

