5.2.4. Recommended Dose Modifications

Every effort should be made to administer study treatment on the planned dose and schedule.

In the event of significant toxicity, dosing may be delayed and/or reduced as described below. In the event of multiple toxicities, dose modification should be based on the worst toxicity observed. Patients are to be instructed to notify investigators at the first occurrence of any adverse symptom.

Dose modifications may occur in three ways:

- Within a cycle: dosing interruption until adequate recovery and dose reduction, if required, during a given treatment cycle;
- Between cycles: next cycle administration may be delayed due to toxicity in the previous cycle;
- In the next cycle: dose reduction based on worst toxicity in the previous cycle.

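### SAP 9.2.4's percent of starting dose uses each cycle's own Day 1 dose as reference, so on a literal reading it cannot show a dose reduction

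*SAP*

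**What the plan says.** Under Treatment Administration/Compliance (SAP 9.2.4), a block introduced by "The following will be summarized for cumulative dose by dose level and cycle" has one bullet. It asks for summary statistics of cumulative dose and of "percent of starting dose (compared to Day 1 dose of each cycle").

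The dosing scheme is in Protocol 5.2.3: "PF-06650808 will be administered on Day 1 of each 21-day cycle", and "A cycle is defined as the time from Day 1 dose to the next Day 1 dose". The SAP agrees: "Day 1 of a cycle is the first date of dose within that cycle". Protocol 5.2.4 provides for reduction between infusions: "In the next cycle: dose reduction based on worst toxicity in the previous cycle". Protocol 5.2.6 sets the size: "Doses should be reduced to the next lowest cohort dose level".

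The same part of SAP 9.2.4 defines a dose reduction by comparing the administered dose with the dose planned for the patient at enrolment, which is a fixed reference. It also tabulates patients with delays, interruptions and reductions, the reasons for them, time on treatment, and the number of cycles before the first delay or reduction. A listing by patient and cycle gives cycle length, planned dose, administered dose, percentage of planned dose, and flags for delay, reduction and interruption. No dose-intensity summary is specified.

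**The concern.** A percentage of starting dose is normally reported to show how far patients have come down from the dose they were assigned. Here the wording in brackets resets the reference at every cycle. With several administrations per cycle, comparing later doses with the Day 1 dose would carry information. With one infusion per cycle there is nothing else to compare.

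At stake is one descriptive summary of tolerability over repeated cycles. Protocol 3.4 says the MTD usually becomes the RP2D if it proves "clinically feasible for long term administration in a reasonable number of patients". The amount of dose delivered relative to assignment in later cycles is natural evidence for that judgement, and this is the summary statistic that appears meant to supply it.

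**Working it through.** The SAP states no figure for this statistic, so there is nothing to reproduce. The check applies each possible derivation to one illustrative patient.

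Inputs from the documents:
- one infusion per cycle, on Day 1 (Protocol 5.2.3);
- reduction by one cohort dose level, at most two reductions outside the first cohort (Protocol 5.2.6);
- dose increments of 30%, 69% or 100% (Protocol 3.2), so adjacent levels are taken to differ by a ratio s of 1.3, 1.69 or 2.0;
- delay of at most 2 weeks, so a cycle of at most 35 days (Protocol 5.2.5).

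Assumed patient: four cycles, full dose in Cycles 1 and 2, one level down in Cycle 3, a second level down in Cycle 4. Cycle 2 is prolonged by 7 days and Cycle 3 by 14 days. Doses relative to assignment are 1, 1, 1/s and 1/s².

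| Derivation | C1 | C2 | C3 | C4 |
|---|---|---|---|---|
| Literal: dose in cycle ÷ that cycle's Day 1 dose, any s | 100% | 100% | 100% | 100% |
| Dose in cycle ÷ assigned dose, s = 1.3 | 100% | 100% | 76.9% | 59.2% |
| Same, s = 1.69 | 100% | 100% | 59.2% | 35.0% |
| Same, s = 2.0 | 100% | 100% | 50.0% | 25.0% |
| Running total ÷ that cycle's Day 1 dose, s = 1.3 | 100% | 200% | 360% | 568% |

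The last row covers the case where cumulative dose means a total across cycles. Cycle 3 is (1 + 1 + 0.769)/0.769 = 3.60 and Cycle 4 is (1 + 1 + 0.769 + 0.592)/0.592 = 5.68. On that derivation a reduction raises the percentage.

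Incomplete infusion: if 70% of an infusion is given (an assumed figure) and the denominator is the prescribed Day 1 dose, the result is 70%. If the denominator is the amount given on Day 1, it is 70/70 = 100%.

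Delay: none of these derivations contains time, so the 7- and 14-day prolongations change nothing in the table. A time-based measure is needed:

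relative dose intensity = (dose given ÷ assigned dose) × (planned days ÷ actual days).

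- Full dose, cycle prolonged by 14 days: 1 × 21/35 = 60%.
- The illustrative patient over four cycles with s = 1.3: mean dose (1 + 1 + 0.769 + 0.592)/4 = 84.0% of plan. Planned time is 84 days and actual time 84 + 7 + 14 = 105 days, so 84.0% × 84/105 = 67.2%.

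**The case against.** The strongest reply is that the bracketed wording is terse and the statistic is named for the starting dose. It could mean that each cycle's Day 1 dose is expressed against the original starting dose. That gives 100, 100, 76.9 and 59.2% in the example, and reductions show. This reading is possible, but the SAP does not state it, and the words used make the Day 1 dose of each cycle the comparator. A programmer would have to choose between derivations that give different tables, so the text needs correcting either way.

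The figure is also not 100% without exception. Protocol Appendix 5 allows infusions to be interrupted, and SAP 6.8 contemplates less than 80% of the planned Cycle 1 dose. With a prescribed-dose denominator, an incomplete infusion would show. This stands, but it concerns incomplete infusions, not reductions.

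A reader might infer that the plan hides every reduction and delay, or that this is its only quantitative exposure summary. The documents do not support either. Cumulative dose is summarised in the same bullet without the disputed denominator, and the section's other tables and its listing by cycle report reductions, delays, reasons and time on treatment.

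A reader might also combine one 30% step with a 14-day delay, (1/1.3) × (21/35) = 46%, and set it against the reported 100%. That describes a single cycle that is both reduced and prolonged, not a patient's overall exposure. If toxicity prolongs a full-dose cycle and the reduction applies to the next one, the pair gives (1 + 0.769)/2 × 42/56 = 66%. The delay factor also has nothing to do with the choice of denominator, whose own effect for that step is 76.9% against 100%.

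**Conclusion.** The point stands as a narrow defect in one descriptive statistic. On the literal reading, percent of starting dose is 100% for every fully given infusion, whatever reductions came before. It conflicts with the SAP's own definition of a reduction: a patient one 30% step down is counted as reduced and shows 100% where the enrolment reference gives 76.9%. With 69% or 100% spacing the correct figure would be 59.2% or 50.0%.

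This rests on reading the brackets as the denominator and on adjacent cohort levels differing by one of the protocol's stated increments. The inability to show delay is a separate matter and would remain under any dose denominator.

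The consequence is small. Protocol 3.4 sets no exposure threshold and names no dose-intensity measure for the RP2D, so it cannot be said that the dose decision would be misled. The DLT and response analyses do not use this statistic.

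**What to change.** In SAP 9.2.4, replace the bracketed comparator with the assigned mg/kg dose, meaning the dose planned at enrolment for Cycle 1 Day 1. This matches the section's definition of a reduction. State whether cumulative dose is the amount within a cycle or a running total, and if it is a running total, scale the denominator to the planned total to date. Name the same reference for the listing's percentage of planned dose.

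Optionally, add relative dose intensity by dose level, from the administered dose and cycle length that the listing already includes. The cost is a line or two of SAP text and, for the option, one derived variable. No new data collection or protocol change is needed.
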